4.2 Contents of the Written Information

The written information for subjects should include explanations regarding the following:

- (1) That the study involves research.
- (2) The purpose of the study.
- (3) The name, title, and contact information of the investigator or subinvestigator.
- (4) Study methods (including aspects of the study that are experimental, inclusion criteria, and the probability for random assignment to each treatment).
- (5) That there is no intended benefit of the study drug on the subject's mental and physical health, and foreseeable inconvenience to the subject.
- (6) The expected duration of the subject's participation in the study.
- (7) That the subject's participation in the study is voluntary and that the subject may refuse to participate or withdraw from the study, at any time, without penalty or loss of benefits to which the subject is otherwise entitled.
- (8) That the monitor(s), auditor(s), IRB, and regulatory authority(ies) will be granted direct access to the subject's original medical records and data, without violating the confidentiality of the subject, to the extent permitted by applicable laws and regulations and that, by signing a written informed consent form, the subject is authorizing such access.
- (9) If the results of the study are published, the subject's identity will remain confidential.
- (10) The person(s) to contact for further information regarding the study and the rights of study subjects, and whom to contact in the event of a study-related injury.
- (11) The compensation and treatment available to the subject in the event of a study-related injury.
- (12) The type of IRB that reviews and discusses the appropriateness of the concerned study, the matters to be reviewed and discussed at the IRB, and other study-related issues for the IRB.
- (13) The approximate number of subjects involved in the study.
- (14) That the subject will be informed in a timely manner if information becomes available that may be relevant to the subject's willingness to continue participation in the study.
- (15) The foreseeable circumstances and reasons under which the subject's participation in the study may be terminated.
- (16) The anticipated expenses, if any, to the subject for participating in the study.

- (17) The anticipated prorated payment, if any, to the subject for participating in the study (including the calculation method of the payment).
- (18) The subject's responsibilities.

4.3 Methods of Obtaining Informed Consent

- (1) Prior to the start of the study, the investigator (or subinvestigator) will provide each prospective subject with an informed consent form and written information approved by the IRB, as well as a thorough explanation regarding the study. Study collaborators can also give supplementary explanations to prospective subjects. The explanation provided to the prospective subjects should be expressed in plain words and expressions, whenever possible so that he/she can easily understand the information. Each prospective subject must be given ample opportunity to inquire about the details of the study and receive answers to his/her satisfaction. The investigator (or subinvestigator) will obtain written consent to participate in the study from each prospective subject at his/her free will, after acquiring a thorough understanding.
- (2) In the informed consent form, the investigator (or subinvestigator) who has provided an explanation and the prospective subject should sign or affix their name and seal with the date of entry. If a study collaborator has provided a supplementary explanation, he/she should also sign or affix his/her name and seal to the form with the date of entry.
- (3) Prior to each subject's participation in the study (screening), the investigator (or subinvestigator) will issue a copy of the signed or named and sealed informed consent form with the date of entry, together with written information to the subject and retain the original, in accordance with the rules at the study site.
- (4) The investigator (or subinvestigator) will record the date of consent and the version of the informed consent form and written information used for explanation in each subject's case report form (CRF).

4.4 Revision of the Informed Consent Form and Written Information

- (1) When any new and important information is obtained that may affect the consent of the subjects, the investigator (or subinvestigator) shall immediately provide the subjects with such information orally, confirm the intention of the subjects to continue participation in the study, and record the results in the medical records.
- (2) Based on the information, the investigator will promptly judge whether it is necessary to revise the informed consent form and written information.
- (3) When the investigator judges it necessary to revise the informed consent form and written information, he/she shall immediately perform these revisions and obtain approval from the IRB.
- (4) The investigator (or subinvestigator) will inform the subjects undergoing the study of such information using the informed consent form and written information that has been newly-approved by the IRB, and obtain a freely given written consent from each subject to continue participation in the study.
- (5) In the same manner as the first consent, the investigator (or subinvestigator) who has provided an explanation and the subject will sign or affix their name and seal

with the date of entry. If a study collaborator has provided a supplementary explanation, he/she should sign or affix his/her name and seal to the form with the date of entry.

- (6) The investigator (or subinvestigator) will issue a copy of the signed or named and sealed informed consent form with the date of entry, together with written information to the subject and retain the original, in accordance with the rules at the study site.
- (7) The investigator (or subinvestigator) will record the date of consent and the version of the informed consent form and written information used for explanation in the CRF.

5. Study Design

5.1 Phase and Type of the Study

Phase of the study: Period I
Type of study: Clinical pharmacology study

5.2 Study Design

5.2.1 Type and Details of Cohorts

[figure not shown]
5.2.1.1 Cohort 1: Drug interaction study

Open-label, add-on study (single dose of a victim drug, multiple doses of an perpetrator drug)

Group 1

	Period I (Dosing: Day 1)	Period II (Dosing: Day 4)	Period III (Dosing: Days 6 to 13)
Victim drugs	Rosuvastatin 10 mg, single dose	Sildenafil 50 mg, single dose	Rosuvastatin 10 mg, single dose (Day 9) Sildenafil 50 mg, single dose (Day 12)
Perpetrator drug	—	—	Edaravone 120mg ^{*)} , multiple doses for 8 days (Days 6 to 13)

[figure not shown]
^{*)} A provisional dose. Doses will be determined based on PK results of MCI-186-J25 study.

Group 2

	Period I (Dosing: Day 1)	Period II (Dosing: Days 3 to 7)
Victim drugs	Furosemide 40 mg, single dose	Furosemide 40 mg, single dose (Day 6)
Perpetrator drug	—	Edaravone 120 mg ^{*)} , multiple doses for 5 days (Days 3 to 7)

^{*)} A provisional dose. Doses will be determined based on PK results of MCI-186-J25 study.

[figure not shown]
5.2.1.2 Cohort 2: Preliminary regimen-finding study

Single-dose, open-label crossover study

[figure not shown]
Group	Period I (Dosing: Day1)	Period II (Dosing: Day 4)	Period III (Dosing: Day 7)
3	Edaravone 90mg ^{*)} , single dose No breakfast after dosing (3 Japanese and 3 Caucasians)	Edaravone 90mg ^{*)} , single dose Start of a meal 1 hour after dosing (3 Japanese)	Edaravone 90mg ^{*)} , single dose Dosing 4 hours after breakfast (3 Japanese)
4	Edaravone 90mg ^{*)} , single dose Dosing 4 hours after breakfast (3 Japanese)	Edaravone 90mg ^{*)} , single dose No breakfast after dosing (3 Japanese and 3 Caucasians)	Edaravone 90mg ^{*)} , single dose Start of a meal 1 hour after dosing (3 Japanese)
5	Edaravone 90mg ^{*)} , single dose Start of a meal 1 hour after dosing (3 Japanese)	Edaravone 90mg ^{*)} , single dose Dosing 4 hours after breakfast (3 Japanese)	Edaravone 90mg ^{*)} , single dose No breakfast after dosing (3 Japanese and 3 Caucasians)

^{*)} A provisional dose. Doses will be determined based on PK results of MCI-186-J25 study.

Japanese subjects :

Caucasian subjects :

5.2.1.3 Study Period and Evaluation Period

Study period: The study period is defined as the period from informed consent to completion of the end-of-study assessment (or to completion or termination of follow-up, for any followed-up subjects).

Screening: Subjects providing informed consent will be screened for eligibility to select subjects meeting all of the inclusion criteria and none of the exclusion criteria (Cohort 1: 66 subjects [32 for Group 1 and 34 for Group 2], with a few reserve subjects; Cohort 2: 9 Japanese and 9 Caucasian subjects with a few reserve subjects).

Evaluation period: Cohort 1: The evaluation period is defined as the period from completion of dosing of the study drug or victim drugs (rosuvastatin, sildenafil, and furosemide) on Day 1 to completion of the end-of-study assessment. The duration of hospitalization will be 16 days and 15 nights (Day -1 to Day 15) for Group 1, and 10 days and 9 nights (Day -1 to Day 9) for Group 2.
Cohort 2: The duration of hospitalization will be 10 days and 9 nights (Day -1 to Day 9) for Japanese subjects, and 4 days and 3 nights (Period I, Day -1 to Day 3; Period II, Day 3 to Day 6; Period III, Day 6 to Day 9) for Caucasian subjects.

End-of-study assessment: The prespecified observations and tests will be performed as the end-of-study assessment, 7 days (\pm 2 days) after the last dose of the study drug.

[Rationales for setting]

(1) Cohort 1

In this study, drug interactions will be assessed for enzymes and transporters specified in FDA's DDI (drug-drug interactions) Draft Guidance 2017 as requiring DDI assessment.

An open-label, add-on study has been considered appropriate because the objective of this cohort is to evaluate the effects of drug-drug interactions on pharmacokinetics. Drug interactions will be assessed between the perpetrator drug in a steady state reached by multiple doses of it and the victim drugs. This assessment will be performed based on PK parameter changes obtained by single doses of the victim drugs.

Group 1: When edaravone was incubated with human hepatocytes for 48 hours, edaravone increased mRNA expression of CYP3A at high concentration, which indicated that edaravone had induced CYP3A4 at high concentration. This finding suggests that oral edaravone may cause drug interactions with CYP3A4 substrates by inducing CYP3A4 in intestinal epithelial cells. Moreover, edaravone showed its inhibitory effect on the BCRP transport activity, with IC₅₀ of 121

$\mu\text{mol/L}$. This finding suggests that oral edaravone may cause drug interactions with BCRP substrates by inhibiting BCRP in intestinal epithelial cells. Sildenafil and rosuvastatin are specified as typical substrates of CYP3A and BCRP in the FDA's DDI Draft Guidance. Objective of this group is to assess the effects of multiple doses of edaravone on CYP3A and BCRP activities, with sildenafil and rosuvastatin as the substrates.

Group 2: Sulfate conjugate and glucuronide conjugate of edaravone showed their inhibitory effects on the OAT3 transport activity, with their IC_{50} of $2.74 \mu\text{mol/L}$ and $> 100 \mu\text{mol/L}$ (the remaining transport activity was 67.6% at $100 \mu\text{mol/L}$). This finding suggests that sulfate conjugate and glucuronide conjugate of edaravone may cause drug interactions with OAT3 substrates by inhibiting OAT3. Furosemide is known as an OAT3 substrate. The objective of this group is to assess the effects of the sulfate conjugate and glucuronide conjugate on the OAT3 activity for multiple doses of edaravone, with furosemide as the substrate.

(2) Cohort 2

Crossover study design has been chosen because it allows precise evaluation in a small number of subjects.

In the phase I study (MT-1186-J01 study), when edaravone was administered 30 minutes after a meal, C_{max} and AUC of plasma edaravone decreased to 19.4% and 39.5% of those obtained when it was administered in the fasting state, respectively. When a meal was eaten 30 minutes after edaravone was administered at the same dose, C_{max} and AUC of plasma edaravone decreased to 78.2% and 66.2% of those obtained when it was administered in the fasting state, respectively. For the purpose of finding appropriate administration timing in clinical practice, assessment will be conducted on pharmacokinetics of edaravone obtained when a meal is taken 1 hour after edaravone administration and those obtained when it is administered 4 hours after a meal.

In the phase I study (MT-1186-J01 study), C_{max} and AUC of plasma edaravone in Caucasian subjects were 75% and 79% of those in Japanese subjects, respectively. For the purpose of assessing the difference between races further, a group of Caucasian subjects have been established.

5.3 Methods of Blinding and Randomization

5.3.1 Blinding Methods

This study will be conducted as an open-label study.

5.3.2 Methods of Randomization and Allocation

Randomization will be performed only in Cohort 2. The person in charge of subject assignment will create a randomization key code table and provide it for the investigator. After all subjects are given their own subject identification (ID) code, and identification of subjects and standby subjects are completed (inclusion order for standby subjects will

be determined in advance), the investigator (or subinvestigator) will assign the subjects to Group 3, 4, or 5 in ascending numerical order of subject ID code, and give a randomization number to each subject. The randomization numbers will be recorded in the CRF. If a subject is replaced by a standby subject in the final selection of subjects, subject ID codes and inclusion order for standby subjects that have been determined in advance will be parallelized in ascending numerical order after which a replacement will be conducted. The Investigator (or subinvestigator) or study collaborator will submit a copy of the randomization key code table to the sponsor. The investigator (subinvestigator) will start prescription in accordance with each of the dosage planned for each assigned group, i.e. no breakfast after dosing, dosing 4 hours after a meal, or start of a meal 1 hour after dosing. Details of randomization will be specified in documented subject assignment procedures.

5.4 Endpoints

5.4.1 Safety Assessments

- (1) Adverse events and adverse drug reactions
- (2) 12-lead ECG
- (3) Laboratory tests
- (4) Vital signs
- (5) Sensory tests

5.4.2 Pharmacokinetic Assessments

- (1) Drug concentration (in plasma)

Plasma drug concentration

Unchanged edaravone, sulfate conjugate, and glucuronide conjugate (only in Group 2 of Cohort 1 and Cohort 2)

Unchanged rosuvastatin (in Group 1), unchanged sildenafil (in Group 1), and unchanged furosemide (in Group 2)

- (2) Pharmacokinetic parameters

Cohort 1

Unchanged edaravone, sulfate conjugate (in Group 2), and glucuronide conjugate (in Group 2): AUC_{0-t} , AUC_{0-24} , $AUC_{0-\infty}$, C_{max} , t_{max} , $t_{1/2}$, Kel , MRT^* , CL/F^* , V_z/F^* , and V_{ss}/F^* , after administration of edaravone alone and after administration of edaravone in combination with each drug (*: To be calculated only for unchanged edaravone)

Unchanged rosuvastatin (in Group 1), unchanged sildenafil (in Group 1), and unchanged furosemide (in Group 2): AUC_{0-t} , AUC_{0-24} , $AUC_{0-\infty}$, C_{max} , t_{max} , $t_{1/2}$, Kel , MRT , CL/F , V_z/F , and V_{ss}/F , after administration of each victim drug alone and after administration of each victim drug in combination with edaravone

Cohort 2

AUC_{0-t} , AUC_{0-24} , $AUC_{0-\infty}$, C_{max} , t_{max} , $t_{1/2}$, Kel , MRT^* , CL/F^* , V_z/F^* , and

V_{ss}/F^* (*: To be calculated only for unchanged edaravone)

[Rationales for setting]

Parameters needed in pharmacokinetic assessment were selected in compliance with “Methods of Drug Interaction Studies” [June 4, 2001, Pharmaceutical and Medical Safety Bureau/Evaluation and Licensing Division (PMSB/ELD) Notification No. 813] and with reference to “Clinical Pharmacokinetics Studies on Drugs” (June 1, 2001, PMSB/ELD Notification No. 796) and “Guideline for Bioequivalence Studies of Generic Products” [February 29, 2012, Pharmaceutical and Food Safety Bureau/Evaluation and Licensing Division (PFSB/ELD) Notification No. 0229-10].

6. Sample Size and Planned Study Period

6.1 Sample Size

Total of 84 subjects

Cohort 1: 66 subjects (32 for Group 1, 34 for Group 2)

Cohort 2: 18 subjects (9 Japanese and 9 Caucasian subjects)

[Rationales for setting]

(1) Cohort 1

Because there is no information about pharmacokinetic parameters for coadministration of each victim drug (rosuvastatin, sildenafil, or furosemide) and edaravone, the number of subjects for each group was set as follows based on data about C_{max} and AUC after administration of victim drugs obtained from previous studies and literatures.

- Group 1

Regarding rosuvastatin, based on results of previous studies, geometric CV (intra-individual) of C_{max} and $AUC_{0-\infty}$ was hypothesized to be 21.0% and 23.0%, respectively. On the assumption that when only rosuvastatin is administered and when it is coadministered with edaravone, ratio of both parameters would be 1.00; the number of subjects was calculated to be 20 which would allow power of at least 80% in 2 one-tailed tests with significance level of 5%.

Regarding sildenafil, based on results of previous studies, geometric CV (intra-individual) of C_{max} and $AUC_{0-\infty}$ was hypothesized to be 28.9% and 22.8%, respectively. On the assumption that when only sildenafil is administered and when it is coadministered with edaravone, ratio of both parameters would be 1.00; the number of subjects was calculated to be 29 which would allow power of at least 80% in 2 one-tailed tests with significance level of 5%.

Based on the above results, the target number of subjects was set at 32, which is the total of 3 (an anticipated number of subjects who might withdraw from the study) and 29 (the number of subjects calculated based on sildenafil data).

- Group 2

Based on results of previous studies, intra-individual geometric CV of C_{max} and $AUC_{0-\infty}$ of furosemide was hypothesized to be 29.5% and 11.5%, respectively. On the assumption that when only furosemide is administered and when it is coadministered with edaravone, ratio of both parameters would be 1.00; the number of subjects was calculated to be 31 which would allow power of at least 80% in 2 one-tailed tests with significance level of

5%. Based on the above results, the target number of subjects was set at 34 on the basis that 3 subjects might withdraw from the study.

Based on the above, the target number of subjects was set at 66 for Cohort 1 (32 for Group 1, 34 for Group 2).

(2) Cohort 2

The target number of subjects was set on the assumption that it would allow obtaining results that will meet the study objectives although it is not based on statistical calculations.

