13.4.2 Pharmacokinetics

For the plasma concentrations of unchanged edaravone, sulfate conjugate, and glucuronide conjugate, and each victim drug (only for Cohort 1), descriptive statistics for each period and time after dosing will be calculated for each Cohort, Group, and dosing condition. In addition, descriptive statistics will be calculated for the PK parameters (e.g., C_{max} , t_{max} , AUC, and $t_{1/2}$) of unchanged edaravone, sulfate conjugate, glucuronide conjugate, and each victim drug for each Cohort, Group, and dosing condition.

In order to evaluate effects of edaravone on victim drug pharmacokinetics, log-transformed $AUC_{0-\infty}$, AUC_{0-t} , and C_{max} of the victim drugs will be analyzed as follows. The analysis will be performed for each group using a linear mixed-effects model with dosing conditions as fixed effects and subjects as random effects. Ratios for $AUC_{0-\infty}$, AUC_{0-t} , and C_{max} between victim drug combined with edaravone and victim drug alone will be calculated. For these ratios, least square means and 90% confidence intervals (CIs) will be calculated. If the 90% CI ranges between 0.80 to 1.25, it will be judged that edaravone has no effects on victim drug pharmacokinetics, according to the Drug Interaction Guideline for Drug Development and Labeling Recommendations.

In order to evaluate effects of a meal on edaravone pharmacokinetics when edaravone is orally administered, log-transformed $AUC_{0-\infty}$, AUC_{0-t} , and C_{max} of edaravone will be analyzed as follows. The analysis will be performed using a linear mixed-effects model with dosing conditions, duration, and the groups as fixed effects and subjects as random effects. Ratios for $AUC_{0-\infty}$, AUC_{0-t} , and C_{max} between dosing conditions, i.e. between dosing 4 hours after a meal/start of a meal 1 hour after dosing and no breakfast after

dosing. For these ratios, least square means and 90% CIs will be calculated. If the 90% CI ranges between 0.80 to 1.25, it will be judged that the meal has no effects on edaravone pharmacokinetics when edaravone is orally administered.

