#### *PK Parameters*

The following PK parameters for rosuvastatin, sildenafil, and furosemide will be calculated from measured plasma concentrations:  $AUC_{0-t}$ ,  $AUC_{0-24}$ ,  $AUC_{0-\infty}$ ,  $C_{\text{max}}$ ,  $t_{\text{max}}$ ,  $t_{1/2}$ ,  $\text{Kel}$ ,  $\text{MRT}$ ,  $\text{CL/F}$ ,  $V_z/F$ ,  $V_{ss}/F$

All PK parameters will be summarised by analyte alone and in combination with edaravone.

These parameters will also be listed. For all PK profiles for which the Kel has been calculated, the following will be listed:

- Number of data points used in the regression analysis for estimation of Kel.

- The lower and upper limits of the time period spanned by the data points used in the regression analysis for estimation of  $K_{el}$ .
- Adjusted R-squared value.
- Percentage of  $AUC_{0-\infty}$  extrapolated.

For  $C_{max}$ ,  $AUC_{0-t}$ ,  $AUC_{0-24}$  and  $AUC_{0-\infty}$  spaghetti plots will be produced showing individual changes from victim drug alone to victim drug + edaravone.

For  $C_{max}$ ,  $AUC_{0-t}$ ,  $AUC_{0-24}$  and  $AUC_{0-\infty}$  ratios (victim drug + edaravone / victim drug alone) will be calculated for each subject. These will be listed and summary statistics (N, n, mean, SD, median, minimum, maximum) for these will also be presented.

$C_{max}$ ,  $AUC_{0-t}$ ,  $AUC_{0-24}$  and  $AUC_{0-\infty}$  will be analysed as for the assessments of effect on pharmacokinetics of rosuvastatin, sildenafil, and furosemide by edaravone as explained in 7.9.3, but 90% CI for the ratio of  $AUC_{0-t}$  and  $AUC_{0-24}$  will not be used for the assessment of the effect of edaravone on rosuvastatin, sildenafil and furosemide.

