#### *Statistical Analysis:*

A linear mixed effects model will be fitted to log-transformed PK parameters ( $AUC_{0-t}$ ,  $AUC_{0-24}$ ,  $AUC_{0-\infty}$ , and  $C_{max}$ ) including treatment as fixed effect and subject as random effect. Treatment will be victim drug + edaravone or victim drug alone. Estimates of mean difference between treatments will be obtained with 90% CI for the difference. These estimates and limits will then be back-transformed to obtain ratios of least squares geometric means A 90% CI for the ratio of  $AUC_{0-\infty}$  as well as  $C_{max}$  which lie entirely within the limits of 0.80 to 1.25 provides evidence of no effect of edaravone on rosuvastatin, sildenafil and furosemide.

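### The 80% power stated for sildenafil at 29 evaluable subjects is for Cmax alone; the SAP's rule needs AUC0-inf as well, which gives about 77% to 80%

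*Protocol*

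**What the plan says.** Protocol 6.1, repeated in SAP 7.3, sizes Group 1 on sildenafil. The geometric within-subject CV of Cmax and AUC0-inf "was hypothesized to be 28.9% and 22.8%, respectively", and the assumption is that the "ratio of both parameters would be 1.00". From this the plan states that "the number of subjects was calculated to be 29 which would allow power of at least 80% in 2 one-tailed tests", each test at the 5% level. Three anticipated withdrawals are added, which gives 32. Neither section says whether the 80% is for one parameter or for both together.

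Protocol 13.4.2 lists AUC0-inf, AUC0-t and Cmax and gives the criterion: "If the 90% CI ranges between 0.80 to 1.25, it will be judged that edaravone has no effects on victim drug pharmacokinetics". It does not say how the parameters combine.

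SAP 7.9.3 does. It asks for a 90% confidence interval for AUC0-inf and likewise for Cmax "which lie entirely within the limits of 0.80 to 1.25 provides evidence of no effect of edaravone on rosuvastatin, sildenafil and furosemide". SAP 7.9.1 adds that the intervals for AUC0-t and AUC0-24 "will not be used for the assessment of the effect of edaravone on rosuvastatin, sildenafil and furosemide". SAP section 1 states that its analysis details take precedence over the protocol's. The operative rule is therefore two parameters, both of which must pass.

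**The concern.** The power statement and the decision rule do not refer to the same event. The 80% is the chance that one interval falls within the limits, whereas the conclusion needs two. Joint power cannot exceed the smaller of the two single-parameter powers, and it equals that smaller value only when the parameters are almost perfectly correlated. The smaller value for sildenafil is already 80.0%, so any further requirement tends to take the total below the stated minimum.

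The number matters because 29 is what the design is built to preserve after withdrawals. If the trial ends there, the chance of concluding no effect on sildenafil when there truly is none may be a little lower than a reader of either section would believe.

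**Working it through.** **Inputs.** CV 28.9% for Cmax and 22.8% for AUC0-inf, true ratio 1.00, 5% per one-sided test, n = 29 (Protocol 6.1, SAP 7.3). Limits 0.80 to 1.25, both parameters required, model with treatment fixed and subject random (SAP 7.9.3). With two measurements per subject this is a paired comparison with n - 1 degrees of freedom. The correlation between the two within-subject log differences, rho, is in neither document; it is assumed to lie between 0 and 1.

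**Formulas.** Within-subject SD on the log scale: s = sqrt(ln(1 + CV^2)). Standard error of the mean log difference: SE = s x sqrt(2/n). Both limits are at distance ln 1.25 = 0.2231 from zero. Power is the probability that the absolute estimated difference plus t(0.95, n - 1) times the estimated SE is below 0.2231, integrated over the distribution of the estimated variance.

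**Step 1: reproduce the plan's figure.**
- Cmax: s = sqrt(ln(1 + 0.289^2)) = 0.2832; SE = 0.2832 x sqrt(2/29) = 0.0744; t with 28 df = 1.701. Hand approximation: 0.2231/0.0744 - 1.701 = 1.30, and 2 x Phi(1.30) - 1 = 0.806. The exact power is 0.800; at n = 28 it is 0.781.
- AUC0-inf: s = sqrt(ln(1 + 0.228^2)) = 0.2251; SE = 0.0591. Exact power is 0.958. Alone, this parameter would need only 19 subjects for 80%.

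The stated 29 therefore reproduces, to rounding, as the size for Cmax alone. The other two victim drugs show the same pattern. Rosuvastatin's 20 gives 82.3% for its more variable parameter (AUC0-inf), and furosemide's 31 gives 81.5% for its more variable parameter (Cmax).

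**Step 2: power for both parameters.** If rho = 0, the powers multiply: 0.800 x 0.958 = 0.767 (rounded from 0.8000 x 0.9583 = 0.7666). If rho = 1, joint power equals the smaller one, 0.800. Values in between come from simulating the paired means and their covariance matrix, 400,000 runs per cell. The simulation standard error is about sqrt(0.8 x 0.2/400,000) = 0.0006, or 0.06 points.

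| Evaluable n | Cmax alone | AUC0-inf alone | Joint, rho 0 | Joint, rho 0.5 | Joint, rho 0.8 | Joint, rho 1 |
|---|---|---|---|---|---|---|
| 29 | 80.0% | 95.8% | 76.7% | 77.8% | 79.3% | 80.0% |
| 30 | 81.8% | 96.4% | 78.9% | 79.8% | 81.2% | 81.8% |
| 31 | 83.4% | 97.0% | 80.9% | 81.7% | 83.0% | 83.4% |
| 32 | 84.9% | 97.4% | 82.7% | 83.4% | 84.5% | 84.9% |

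Using n - 2 degrees of freedom moves the results at 29 by only about 0.1 to 0.2 points.

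**Step 3: translate to withdrawals from 32.** With one withdrawal (31), joint power is at least 80% at any correlation from 0 up. With two (30), it reaches 80% only from a correlation of about 0.6 (80.3% there). With three (29), it is below 80% except in the limit of very high correlation; the gap is 80.0 - 76.7 = 3.3 points at most and about 0.1 at a correlation of 0.9.

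**Step 4: furosemide.** AUC0-inf power at 31 is about 100%, so joint power equals the Cmax power of 81.5%. The statement for that drug holds under the joint rule.

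**The case against.** The best defence is that nothing was miscalculated. Two one-sided tests are the standard equivalence procedure for one parameter, the plan gives a separate CV for each parameter, and 29 follows from the larger one. Neither document claims joint power. This stands: a reader might infer an arithmetic error in the 29, and there is none. The fault is that the sections do not say which parameter the power belongs to, while the SAP states a rule that needs two.

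A second objection is that the shortfall depends on a correlation the documents do not give. This also stands, so the result has to be given as a range. Cmax and AUC0-inf come from the same concentration profile, so the independence end is a worst case among non-negative correlations, not an expectation.

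Third, the planned 32 already covers the joint rule, and a shortfall across the range needs all three withdrawals. That is correct and limits the consequence. It can be added that SAP 7.9 and section 8 keep subjects with PK data from only one treatment period. This helps little, since such a subject adds little to a within-subject contrast.

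A reader might also extend the point to rosuvastatin's 20. The documents do not support that as a finding. Joint power at 20 runs from about 74% to 82% and passes 80% at a correlation of about 0.9. Moreover, the 20 did not set the group size: at the 29 that did, rosuvastatin's joint power is about 94% to 96%.

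**Conclusion.** The point holds as a minor mismatch between the power statement and the decision rule. At 29 evaluable subjects, 80% is the power for sildenafil Cmax alone. Joint power is 76.7% to 80.0% for correlations from 0 to 1, and about 78% to 79% for correlations of 0.5 to 0.8. This rests on the plan's own CVs, a true ratio of 1.00 for both parameters, the paired model, and an assumed non-negative correlation.

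A reader might infer that Group 1 is too small. That does not follow: joint power at the planned 32 exceeds 80% throughout the assumed range. What the allowance of three withdrawals does not do is guarantee 80% for the joint conclusion. It does so for one withdrawal, and for two only if the correlation is about 0.6 or more.

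**What to change.** In Protocol 6.1 and SAP 7.3:

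- Say that 29 evaluable subjects give 80% power for sildenafil Cmax alone.
- Add the joint power for Cmax and AUC0-inf under the SAP 7.9.3 rule, with the assumed correlation stated: about 77% to 80% at 29 for correlations from 0 to 1.
- Note that 31 evaluable subjects give at least 80% jointly at any non-negative correlation, so that 32 enrolled guarantees this with one withdrawal, and with two only if the correlation is about 0.6 or more.

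The furosemide figure can stay, and rosuvastatin's 20 needs no action on this ground. The cost is a few sentences and a slightly less favourable stated power. Enrolment, model, limits and decision rule remain as they are.
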